**To determine the functional significance of the treatment, patient perception and satisfaction with recovery**

- Along with degree of successful reintegration will be evaluated using Likert scores. Regression models will be created to evaluate the effect of mindfulness on perception of recovery and patient satisfaction at each time point. Within regression models, we will include traditional markers of recovery (mRS and BI) to determine the independent effect of mindfulness training on satisfaction and quality of life.

d. Early stopping rules: the study will be stopped if the participant is unable to tolerate the MEG or MBSR.

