We will recruit a cohort of patients with minor stroke (NIHSS <8, modified Rankin score 0-2). Following baseline assessment of depression, fatigue, cognition, functional status, and patient satisfaction, individuals will be randomized to a standard 8 week MBSR course aimed at improving attention and concentration, and reducing anxiety and depression, or a bi-monthly standard Stroke Support Group (SSG). All patients will undergo reassessment post-intervention (~4-6 months post-infarct), along with MEG pre- and post-intervention. Participants will undergo neuroimaging pre- and post-intervention. We will evaluate differences in activation patterns and functional connectivity both at rest and during a visual cognitive task. We hypothesize that both groups will initially exhibit abnormal frontal lobe function compared to controls; however, after MBSR this will improve versus the SSG group.

Participants will also be administered a pre- and post-intervention Montreal Cognitive Assessment (MoCA), along with a battery of cognitive tasks to measure attention, concentration, processing speed, and executive function. Performance will be compared pre- and post-intervention, and for MBSR versus SSG participants. We hypothesize scores will be significantly better following MBSR compared to the SSG group. Finally, the PHQ9 and other measures of patient-reported outcomes (eg., mood) will be given to patients pre- and post-intervention and compared across groups at each time point. We hypothesize MBSR will improve rates of depression/anxiety compared to SSG. We will also evaluate patient satisfaction scores, measures of functional recovery: the modified Rankin scale (mRS) and Barthel Index (BI), and the likelihood of successful return to work. Individuals with minor stroke have tremendous potential to return to their baseline level of function, though often struggle. If effective in reducing post stroke mood and cognitive disorders for those with minor stroke, allowing them to return to work, MBSR will significantly reduce post-stroke morbidity and improve quality of life.

---

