**Objective 2: To determine the impact of mindfulness training on post-stroke cognitive impairment.**

Participants will be administered a pre- and post-intervention Montreal Cognitive Assessment (MoCA), along with a battery of cognitive tasks to measure attention, concentration, processing speed, and executive function. Performance will be compared pre- and post-intervention, and for MBSR versus SSG participants.

**Objective 3: To determine the impact of mindfulness training on post-stroke depression.** The PHQ9 will be given to patients pre- and post-intervention and compared across groups at each time point.

*As secondary objectives we will also evaluate patient satisfaction scores, measures of functional recovery: the modified Rankin scale (mRS) and Barthel Index (BI), and the likelihood of successful return to work.*

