## 7. Study Statistics

- a. Primary outcome variables include: MEG- changes in spectral properties and an estimate of the localization of spontaneous brain activity during resting state, functional connectivity during resting state. Clinical- performance on the MOCA and other cognitive measures (as part of the Recovery Study), patient-reported outcomes: fatigue, depression, satisfaction, quality of life.
- b. Secondary outcome variables include: changes in spectral properties, spontaneous brain activity, and functional connectivity during completion of various cognitive tasks.
- c. We will use an intention-to-treat analysis; however, we will adjust for degree of participation and consider an additional exploratory per-protocol analysis. For those lost-to-follow-up, data will be censored at the time they are lost. In addition to the proposed analyses, if there is evidence for an uneven distribution of confounding factors across treatment and control groups, we will perform multivariable linear regression to adjust for confounders (eg. degree of participation, age, sex, level of education, antidepressant use, and major medical co-morbidities (Charlson Comorbidity Index)).

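### The satisfaction and quality-of-life regressions include mRS and BI without fixing the visit; if follow-up values are used, the arm coefficient is neither the total effect of MBSR nor a clean direct effect

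*Combined protocol and SAP*

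**What the plan says.** The last analysis block of section 7 (functional significance, perception and satisfaction) has two relevant sentences. The first sets the aim: "Regression models will be created to evaluate the effect of mindfulness on perception of recovery and patient satisfaction at each time point". The second adds the covariates: "Within regression models, we will include traditional markers of recovery (mRS and BI) to determine the independent effect of mindfulness training", with satisfaction and quality of life as the outcomes. It names no visit for mRS and BI.

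Elsewhere the same scales are outcomes. The secondary objectives in section 2 include "measures of functional recovery: the modified Rankin scale (mRS) and Barthel Index (BI), and the likelihood of successful return to work", and the Abstract says the same.

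The standing of the dependent variables differs by section. Section 7a lists "patient-reported outcomes: fatigue, depression, satisfaction, quality of life" among the primary outcome variables, while section 2 places satisfaction under the secondary objectives.

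Nothing in the documents limits the mRS and BI covariates to baseline, commits to a satisfaction or quality-of-life model without them, or labels the adjusted model as mediation.

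**The concern.** The plan treats function both as something MBSR might improve and as something to hold fixed when measuring what MBSR does. The scales are described as markers of recovery and the models are fitted at each time point, so the most natural reading is that the post-intervention model uses post-intervention mRS and BI.

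On that reading two things go wrong. A patient who is more satisfied because MBSR improved function has that gain credited to mRS and BI and not to MBSR. In addition, comparing patients with equal follow-up function is no longer a randomised comparison: if something unmeasured drives both function and satisfaction, the arms differ on it once follow-up function is held fixed.

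The Abstract expects that, if effective, "MBSR will significantly reduce post-stroke morbidity and improve quality of life", and section 7 says the results will supply treatment-effect estimates for a larger trial. A coefficient of this kind, carried forward as the effect of MBSR, would be the wrong input.

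**Working it through.** **Plan's own figure.** None is attached to these regressions. The only design number is at least 20 per group. It cannot be reproduced, because alpha, power, effect size and SD are not given.

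**Model.** Let A be arm (MBSR = 1, stroke support group = 0) and Y the follow-up outcome. Let M be follow-up function, one score standing for mRS and BI, with higher better and within-arm SD 1. Let U be an unmeasured shared cause with SD 1.

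- M = aA + 0.5 × (baseline function) + dU + error
- Y = τA + bM + cU + error

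The total effect of MBSR is τ + ab. Given A and M, the expected value of U is d(M − aA), so the coefficient on A with M in the model is τ − acd. The shift from the total effect is therefore

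(τ − acd) − (τ + ab) = −a(b + cd).

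It is downward when MBSR improves function (a > 0), better function improves the outcome (b > 0), and the shared cause acts the same way on both (cd ≥ 0). It is zero when a = 0. All values below are assumptions; the documents give none.

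**No shared cause (cd = 0), total effect held at 0.60 SD**

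| a | b | shift = −ab | adjusted coefficient |
|---|---|---|---|
| 0.6 | 0.5 | −0.30 | 0.30 |
| 0.6 | 0.4 | −0.24 | 0.36 |
| 0.2 | 0.5 | −0.10 | 0.50 |
| 0.1 | 0.5 | −0.05 | 0.55 |
| 0 | 0.5 | 0 | 0.60 |

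**With a shared cause (c = d = 0.6, so cd = 0.36), τ = 0.3, b = 0.5**, outcome error SD 1

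| a | total = 0.3 + 0.5a | adjusted = 0.3 − 0.36a | simulated mean of adjusted coefficient |
|---|---|---|---|
| 0.5 | 0.55 | 0.120 | 0.116 |
| 0.2 | 0.40 | 0.228 | 0.233 |
| 0 | 0.30 | 0.300 | 0.302 |

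The simulations used 20 per arm and 6,000 replicates per row. Where a is not zero, the adjusted coefficient also misses the direct effect of 0.3, so calling it a direct effect does not rescue it.

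**Check of the remedy.** With τ = 0.3, a = b = 0.5 and no shared cause, the true total effect is 0.550. The simulated mean was 0.549 with no covariate, 0.551 adjusting for baseline function only, and 0.301 adjusting for follow-up function. Baseline adjustment leaves the total effect intact.

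**The case against.** The strongest reply is that the visit is inferred. The two sentences are separate, only the first mentions time points, and if baseline mRS and BI were meant the bias disappears. That stands as a limit on confidence. It does not remove the need to say which visit is meant.

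Second, the plan asks for an independent effect, which is a direct-effect question and a legitimate one. The first sentence could also be read as a model without mRS and BI. But no such model is committed to, and a direct effect needs an assumption of no unmeasured confounding between function and outcome, which is not stated.

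Third, function may barely move. Entry requires mRS 0-2, and section 8 requires functional independence for the MEG visits. This stands: the shift is proportional to a, and at a = 0.1 it is 0.05 in the first table.

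Fourth, likely shared causes are measured: mood by PHQ-9, and comorbidity by the Charlson index. That is partly fair. Neither is named for these models, although section 7c would add the Charlson index if the arms are unbalanced. Follow-up mood is itself expected to respond to MBSR, so adjusting for it would repeat the problem.

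A reader might also infer that the bias could go either way in this trial. Algebraically it can: a = 0.5, b = 0.2, c = −0.8, d = 0.7 turns a total of 0.40 into 0.58. That needs a shared cause that improves function while lowering satisfaction, or the reverse, and the documents suggest none. An upward shift would also arise if MBSR worsened function, which the plan does not expect.

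**Conclusion.** The point holds, subject to the unstated visit. If follow-up mRS and BI enter these models, the arm coefficient is not the total effect of MBSR, and it is a valid direct effect only if function and outcome share no unmeasured cause. The expected direction is downward, given that MBSR helps function and shared causes act alike on both.

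The size cannot be fixed from the documents. Without a shared cause, the assumed cases run from no loss at a = 0, through 0.05 to 0.10 at a = 0.1 to 0.2, up to 0.24 to 0.30 of a 0.60 SD effect at a = 0.6. The upper end should not be presented as the likely result in patients who enter at mRS 0-2.

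A reader might go further and say that the plan openly prescribes a wrong estimand for a primary outcome. The text does not support that: the visit is open, the stated target is an independent effect, and satisfaction is primary in section 7a but secondary in section 2. A claim of lost power is not made either, since the adjusted and unadjusted tests address different effects.

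**What to change.** Reword the block in section 7 as follows:

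- **Main model.** Regress follow-up satisfaction or quality of life on arm (MBSR versus support group), adjusting only for values taken before randomisation: the baseline score where collected, and baseline mRS and BI. Report this arm coefficient as the effect of MBSR.
- **Model with follow-up mRS or BI.** Keep it, if wanted, as a labelled exploratory mediation analysis. State its assumption of no unmeasured confounding, and do not report its arm coefficient as the effect of MBSR.
- **Pre-intervention time point.** Present it as a description of baseline. No effect of mindfulness can exist before the intervention.

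Sections 2 and 7a should also agree on whether satisfaction is primary or secondary.

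The cost is wording only. The Abstract plans baseline assessment of functional status and satisfaction before randomisation, and mRS is needed for eligibility. The team should confirm that BI and quality of life are among the baseline measures, since neither is named there. No extra visits or participants are needed.

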## 8. Risks

- Participants have had minor strokes and are recovering well without severe neurological deficits but we acknowledge the following relative risks:
  - MEG- there are few to no medical risks with MEG. We will not be imaging pregnant women. The major risk is claustrophobia, though the machine is relatively open and in a large room, and boredom. MEG personnel will show the MEG, explain that it is only a recording device, does not make noise, and carefully describe the testing procedure to each subject before recording the head shape, applying the fiducial markers and initiating MEG recording. MEG personnel will be in audio contact with the subject during the recording and be able to see them through a video link. If any subject experiences stress or discomfort the study can be stopped at any time. In addition, the MEG scanner uses helium. It is truly a remote possibility that the liquid helium may boil off rapidly and fill the recording room with extremely cold dense gaseous helium, which can be dangerous if breathed for more than a few minutes. The MEG operator will clearly notice the quench and immediately provide assistance to anyone inside the recording room. This has never happened in the center's long history of imaging.
  - Travel- Given their relatively good function and outpatient status, there is less risk to travel, despite their relatively recent stroke. In order to take part in the MEG portion of the study patients must be fully functionally independent and able to travel unaccompanied to the University of Maryland.

- MBSR- Mindfulness training is a combination of meditation and yoga and is well tolerated among many groups with chronic medical problems, including physical limitations. However, given the low stroke severity of our patients, we do not anticipate any additional risks above what would be seen in a population without stroke. We will monitor for fatigue, embarrassment, or other unanticipated issues, and adjustments will be made if needed.
- SSG- Support groups can be therapeutic to patients and their families. The major risk is embarrassment; however, while attendance is required and participation will be encouraged, no patient will be forced to share or participate if it makes them uncomfortable.
- Loss of Confidentiality- The potential legal and social risks to the participants relate to the question of confidentiality of information. It is possible that information obtained may adversely affect the subject's legal or social position if not kept strictly confidential. However, subjects will be identified by number, and other measures will be put in place to minimize the risk of loss of confidentiality including but not limited to keeping data on a password protected computer accessible only to the study team.

- b. Unanticipated problems or study deviations will be reported to the IRB by the PI and an action plan will be created to remedy the situation.
- c. All protocol events or deviations will be reported to the PI regardless of the location of their occurrence (JHMI or UMD), in real time. Members of the study team at JHH and UMD will be in communication regularly to discuss any issues, often in real-time as they arise (either in person or by phone on the day of study participation). Monthly, any event and the formulated action plan (as above) will be reviewed by a study team consisting of co-investigators at both campuses through a teleconference.
- d. As outlined below, there will be no direct cost to the patient for participating in the study, and they will be compensated for their time and participation.

## 9. Benefits

- a. Participants taking part in either MBSR or SSG may derive benefit from the intervention. In addition, they will be advancing the field so that future patients with minor stroke will recover faster and more fully.

## 10. Payment and Remuneration

- a. Participants will be recompensed for travel (see below) and also be compensated for their time and participation. They will receive a total of \$400 for full participation in study (\$100 after their first MEG (1 month), \$100 after completion of the intervention (with completion of at least 75% of sessions, \$100 after their second MEG (4-6 months, post-treatment), and \$100 for successful full completion: intervention, pre- and post-MEG, and pre- and post-cognitive testing).

## 11. Costs

- MEG- cost for image acquisition as well as data processing and interpretation will be paid for through research funding by the PI (approximately \$500 per MEG).
- Travel costs- travel costs including travel to and from The University of Maryland will also be paid for by the PI using study funds. Patients may choose to arrive at the facility using a service such as Uber (trip paid for by the study team) or arrive to the facility themselves where they will be reimbursed for gas and parking.
- MBSR- the 8 week program will be provided at no cost to the patient as part of the study protocol.
- Stroke Support Group- SSG occurs bi-monthly and is run by the team at our Comprehensive Stroke Center. No additional funding is required.

### **Changes to the Protocol to Continue Research Without In-Person Visits (in the setting of worsening pandemic)**

**Consent-** We will expand consent to include remote consent facilitated by video conferencing if needed during their video televisit follow-up. The consent will be reviewed with the patient as previously described either by phone or video. Verbal consent will be obtained. They will be provided with a copy of the consent form via email/fax/mail and will send back in their signed copy (following verbal consent).

**Clinic Visits/Testing-** We have adapted the cognitive tasks and testing batteries so that they can be performed remotely via video conferencing and we can see them remotely via telehealth visits for their clinical/research follow-up visits (participants will need a laptop with a camera for remote/telehealth visits).

When remote assessment/therapy is not feasible, we will conduct in-person visits. In that case, prior to each scheduled visit, we will call participants and screen for COVID-19 symptoms and exposure. If a participant reports symptoms or exposure, the in-person visit will be cancelled. In-person visits will be rescheduled pending medical evaluation of signs/symptoms or after 14-day self-quarantine if there was exposure or potential exposure. The research team will reference JHU policies for self-screening and will defer any in-person or on-campus activities if they report COVID-19 symptoms and another member of the team will conduct the visit if possible. During each visit, participants and the research team will wear masks. If they do not provide their own mask, we will provide a disposable mask for them and practice social distancing whenever possible along with proper hand hygiene practices. All assessment/therapy materials and work surfaces (tables, doorknobs) will be disinfected after each session.

**Interventions-** Currently, both the weekly Stroke Support Group and Mindfulness Based Stress Reduction group are in person. If it is safe for in-person encounters, for the added potential benefit of socialization, we will continue to hold them in small groups. We will take all of the necessary safety precautions described above.

In addition, have adapted both interventions so that they can be available over telecommunication platforms (eg. Zoom) depending on the severity of the pandemic over the study period.

**MEG-** The safety steps described above will be implemented for these in-person visits as well. Scanning is limited to the participant and a tech within the large imaging center in a free-standing imaging center on the University of Maryland Campus. If necessary, we will temporarily discontinue MEG scanning should Johns Hopkins (or the University of Maryland) determine it is unsafe to continue given progression of the pandemic and will use cognitive outcomes alone as our outcome measure in these participants in that case.

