**To determine the impact of mindfulness on post-stroke depression:**

- Participants will be administered the PHQ-9 pre- and post-intervention. Paired t-tests will be used to evaluate for significant differences in scores between time points using each score as a continuous variable. Chi square analysis will be used to evaluate presence or absence of moderate depression (PHQ9 score >9). Independent t-tests and chi square analysis will compare scores of MBSR versus SSG participants for each time point.
- *Sample Size.* Based on prior MBSR studies, we anticipate that this will show a greater clinical effect than change in MoCA, giving us more than adequate power to detect differences with this sample size.

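### If MEG is suspended, the fallback to cognitive outcomes alone, read literally, takes unscanned participants out of the analysis of depression and every other non-MEG outcome

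*Combined protocol and SAP*

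**What the plan says.** The rule is in the MEG paragraph of the pandemic section (Changes to the Protocol to Continue Research Without In-Person Visits). Its trigger concerns the scanner only: "we will temporarily discontinue MEG scanning should Johns Hopkins (or the University of Maryland) determine it is unsafe to continue". Its consequence is that the study "will use cognitive outcomes alone as our outcome measure in these participants in that case".

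The rest of the plan keeps cognition and patient-reported outcomes apart:

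- Section 7, item a, names the primary outcomes. After the MEG measures come "Clinical- performance on the MOCA and other cognitive measures (as part of the Recovery Study") and then, as a further group, "patient-reported outcomes: fatigue, depression, satisfaction, quality of life".
- Section 2 gives cognition to Objective 2 and depression to Objective 3: "The PHQ9 will be given to patients pre- and post-intervention and compared across groups at each time point". Satisfaction, mRS, Barthel Index and return to work appear there as secondary objectives.
- The analysis text of section 7 has separate parts for cognition, for depression ("Participants will be administered the PHQ-9 pre- and post-intervention") and for satisfaction and reintegration ("Along with degree of successful reintegration will be evaluated using Likert scores").

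On remote working, the Clinic Visits/Testing paragraph of the pandemic section says: "We have adapted the cognitive tasks and testing batteries so that they can be performed remotely via video conferencing". It also allows the clinical and research follow-up visits to be held by telehealth.

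**The concern.** A scanner closure explains missing MEG data. It does not explain why a depression questionnaire from the same participant should go unused. Yet the fallback names one class of outcome and adds the word *alone*. In the protocol's own vocabulary, that class does not include depression, fatigue, quality of life or satisfaction.

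At stake is Objective 3. An analyst who follows the sentence would leave unscanned participants out of the PHQ-9 comparison, although they were randomised, received the intervention and attended follow-up. In a pilot planned for at least 20 per group, whose stated use is to supply treatment effect estimates for a larger trial, each such loss matters. An analyst who reads the sentence loosely would keep them. The document does not settle the choice, and it should not be made after the data have been seen.

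**Working it through.** The plan gives no figure for this contingency, so there is none to reproduce. The main check is a comparison of texts; the arithmetic only illustrates the possible size.

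**Step 1. Does the fallback, as worded, cover each outcome?**

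| Outcome | Status in the plan | Described as needing MEG? | Inside cognitive outcomes? |
|---|---|---|---|
| MoCA, cognitive battery | Primary (section 7a), Objective 2 | No | Yes |
| Depression, PHQ-9 | Primary (7a), Objective 3 | No, a questionnaire score | No |
| Fatigue, quality of life | Primary (7a) | No | No |
| Satisfaction | Primary (7a), secondary (section 2) | No, Likert scores | No |
| mRS, Barthel Index, return to work | Secondary (section 2) | No | No |

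Only the first row survives a literal reading. The two labels for satisfaction are a separate inconsistency; depression, fatigue and quality of life are not affected by it.

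**Step 2. Does another part of the document restore the lower rows for these participants?** The PHQ-9 statements in sections 2 and 7 carry no MEG condition, and the telehealth provision keeps the visits going. These are general commitments. None mentions the suspended-MEG case, where the specific rule says something narrower.

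**Step 3. Size, if the literal rule were followed.** From the document: at least 20 per group (section 7, sample size text for the MEG objective). Assumed: an affected share of 10%, 25% or 50%, equal in both arms; every affected PHQ-9 left unused; a common SD; two-sided alpha 0.05; normal approximation. The document gives no affected share, PHQ-9 SD, alpha or target effect.

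- The standard error of the arm difference is SD × √(2/n), so its inflation is √(20/n).
- The difference detectable with 80% power, in SD units, is (1.960 + 0.842) × √(2/n).

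| Share affected | n per arm | SE inflation | Detectable difference | Power for a true 0.8 SD |
|---|---|---|---|---|
| 0% | 20 | 1.00 | 0.89 SD | 72% |
| 10% | 18 | √(20/18) = 1.05 | 0.93 SD | 67% |
| 25% | 15 | √(20/15) = 1.15 | 1.02 SD | 59% |
| 50% | 10 | √(20/10) = 1.41 | 1.25 SD | 43% |

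For example, with n = 15: 2.802 × √(2/15) = 2.802 × 0.365 = 1.02.

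**The case against.** The strongest reply is that the sentence sits in the paragraph about MEG and describes what remains once the scan is lost, so *alone* most naturally means without MEG. It does not tell anyone to stop giving questionnaires. Elsewhere, the PHQ-9 is promised before and after the intervention without any MEG condition, follow-up testing belongs to the clinic visits and not to the MEG trips, and section 4, item g, analyses even early drop-outs' data up to the point of leaving. A plan that uses data from people who leave is unlikely to intend discarding questionnaires from people who stay.

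Most of this stands. It makes the shorthand reading plausible and rules out any claim that the sponsor decided to drop data. It does not remove the problem, because the only sentence written for this case is the narrower one.

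A reader might infer three stronger things that the documents do not support:

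- *That collection of the PHQ-9 and other questionnaires ceases.* The sentence concerns which outcome is used, not what is collected.
- *That the PHQ-9 comparison would be biased, because it would rest on people recruited while MEG was open.* Each participant has two scans, the suspension is temporary, and either scan could be missed, so recruitment date does not define the affected group. A site closure also does not depend on arm. What can be argued is lost precision and a narrower population.
- *That the rule independently breaches the intention-to-treat commitment in sections 4 and 7.* The conflict arises only if the literal reading is accepted, and the commitment is equally a reason to prefer the looser one.

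**Conclusion.** The point holds as a defect in a stated rule. Read literally, the fallback excludes unscanned participants from the analysis of one named objective, of three outcomes labelled primary without conflict (depression, fatigue, quality of life), and of satisfaction and the functional measures. Losing the scanner requires none of this.

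The consequence is conditional: it needs a suspension to occur and the sentence to be followed as written. The document does not say that any suspension took place or how many participants it might affect. A short closure could affect almost nobody. The increases of 15% and 41% in the standard error are correct arithmetic on assumed shares of 25% and 50%, and are not estimates for this trial. Section 7's statement that power for the PHQ-9 is more than adequate refers to the planned sample size, so it would not carry over to a reduced one.

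The correction should be made: the loss is avoidable and touches a named objective.

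**What to change.** In the MEG paragraph of the pandemic section, replace the reference to cognitive outcomes alone with a rule such as:

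*If MEG is suspended, all non-MEG outcomes (cognitive, PHQ-9 and other patient-reported outcomes, mRS, Barthel Index, return to work) continue to be collected pre- and post-intervention in both arms. These participants stay in the analysis of every non-MEG outcome; only MEG outcomes are missing.*

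If the sponsor already meant this, the edit only removes an ambiguity. It costs one sentence: the questionnaires and the follow-up visits are already planned, the visits can be held by telehealth, and no instrument, visit or change in care is added. The primary and secondary labels for satisfaction (section 7a against section 2) should be reconciled separately.
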